Protocol: Peripheral Nerve Stimulation for Shoulder Pain: Dose Response

ID: IRB16-00510

NCT02928055

Document Date: 12/18/2020

8.0 Methods and Procedures I:

8.1 Will this research involve the following Social-Behavioral Procedures:

Check all that apply.

Name _____
 Psychological Testing _____
 Surveys/Questionnaires _____

8.2 Will this research involved any of the following Medical Procedures/Considerations:

Check all that apply.

Name _____
 Collection of Biohazardous Substances _____
 Study of Human Biological Materials (i.e. Urine Collection) _____
 Investigation/Approved Devices _____
 Study of Existing Data _____
 Medical Tests, Comparisons, Evaluations _____
 Clinical Assessments (EEG, EKG, SCID, etc.) _____
 Venipuncture (Blood Draw) _____
 Use of investigational devices _____
 Psychological testing _____

8.3 Identify Data Collection types for this study:

Check all that apply.

Name _____
 Audio-Recording/Video-Recording/Photographs _____
 Chart Review - Prospective _____
 Existing/Retrospective Data/Specimens _____
 Interviews, questionnaires or psychological tests _____

Note if you are doing, recordings, Video-Recording/Photographs then subjects will need to sign the MetroHealth Audio-Video Consent form. See the IRB Forms and Templates.

View: 08-01 Methods and Procedures II

8.1 Methods and Procedures II:

8.4 * Please specify in detail the methods and procedures that are involved in this research:

If this field is not completed your protocol will not be reviewed. Do not enter N/A. Please describe what methods and procedures will be involved in this research.

Study Summary: This is a pilot RCT to explore the role of muscle contraction as a mechanism produced by peripheral nerve stimulation (PNS) to reduce hemiplegic shoulder pain (HSP). Thirty subjects will enroll and receive a 3-week course of percutaneous IM PNS at one of 3 doses. Subjects will be randomized to receive the standard IM PNS treatment (15,120 total contractions), IM PNS at half the standard dose (7,560 total contractions), or IM PNS at 1.5 times the standard dose (22,680 total contractions). Dose will be controlled by differing the stimulation time per day (3h, 6h, or 9h) while keeping constant the duty cycle of stimulation. Subjects will be followed for 12 weeks after treatment.

Baseline Variables and Randomization: Baseline data will be collected so that the balance of covariates across the three groups can be evaluated. Each participant will be characterized with respect to demographics, comorbidities, and medication use.

Study outcome measures (see Outcomes Assessment) will be administered to establish baseline levels. Participants are assigned to treatment groups using an adaptive randomization algorithm [76-78] to minimize group imbalances on key patient characteristics: baseline pain (>6 or ≤ 6) [79], duration of pain (≥ 18 months or < 18 months) [5], and age (≥ 55 years or < 55 years). For each assignment, the algorithm calculates the balance of these variables across the groups and makes an assignment that would result in greater balance in the variables across groups.

Percutaneous PNS System: The Sprint PNS System (SPR Therapeutics, Cleveland, OH), also known as the Smartpatch System, will be used to deliver the PNS therapy. The System consists of a small external stimulator, percutaneous lead, and pad. The external stimulator "snaps" on to the pad. The pad has an embedded power source for the System but also serves as the anode. The pad is replaced regularly based on treatment parameters, allowing the investigative team to prescribe the total dosage based upon the number of pads. The single-channel stimulator outputs a biphasic current waveform with current pulse parameter ranges that are suitable for PNS. These electrodes have been used extensively to deliver percutaneous PNS to shoulder muscles. [6-12, 62, 71]

Lead Placement Procedure: The procedure will be performed under a sterile condition. The location and depth of the electrode implant site are determined by monopolar needle stimulation with demonstration of strong contraction of both the middle and posterior deltoid muscles. [6, 9, 62, 70] The introducer loaded with the lead is inserted perpendicular to the skin surface and advanced to the depth (3-4 cm) defined by the monopolar test stimulation. The introducer is then withdrawn with the electrode retained in the muscle by a barb at its tip.

PNS Treatment Protocol: After one week for lead stabilization [80], the Sprint PNS System will be programmed for stimulation. Based on over 30-yrs of experience, the Cleveland FES Center established parameters for safe and effective delivery of PNS (pulse frequency = 12 Hz; pulse amplitude = 20 mA; pulse duration = 5-200 usec (set by clinician); duty cycle = 5-sec ramp-up, 10-sec plateau, 5-sec ramp down, 10 sec off; daily stim time (randomized) = 3, 6, 9 hrs/day; total contraction dose (randomized) = 7560, 15120, 22680 contractions). [81] These parameters provide strong fused comfortable muscle contraction with minimal fatigue. [6-12, 49, 62, 71,82-84] Stimulation frequency and amplitude are fixed. The pulse duration is set to produce strong, comfortable contraction of both the middle and posterior deltoids. A balanced biphasic waveform allows an equal amount of current to flow in either phase, creating a safe net zero charge. [85] In this dose-response study, participants receive 3h, 6h, or 9h of stimulation each day. The stimulator keeps an electronic log for compliance monitoring.

Electrode and Electrode Site Surveillance and Electrode Removal: All caregivers and participants will be trained in the assessment of electrode site and the daily placement of the Sprint Pad. The caregiver conducts daily inspections to detect complications. The nurse coordinator inspects the site for infection and performs motor/sensory threshold testing for lead migration and lead integrity, respectively, at the following times: within 48-72 hrs of lead placement, at the beginning of PNS treatment, and at the end of treatment. Inspection and testing of motor/sensory thresholds and impedance may also occur anytime during the 3-wk PNS treatment period as deemed necessary. At the end of treatment, the electrode is removed by gently pulling on the external portion. All participants undergo radiographic surveillance for retained electrode fragments.

Outcomes Assessment: The primary outcome measure is the worst pain in the prior 7-days (BPI SF-3). Secondary measures include pain interference with ADLs (BPI SF-9); QoL (SF-36); shoulder impairment (isometric voluntary abduction shoulder torque (IVAST), shoulder kinematic analysis, optional Fugl-Meyer Motor Assessment (upper limb)); and measures of central sensitization (mechanical pain thresholds for hyperalgesia, optional pinprick pain thresholds for hyperalgesia, temporal summation of repetitive pin-prick stimuli). Other optional measures include tactile/touch, vibration and thermal/thermal pain detection thresholds, temporal summation of repetitive thermal stimuli, and Conditioned Pain Modulation (CPM). Details for each measure are presented below. The outcomes are administered face-to-face in a blinded manner.

Brief Pain Inventory SF-3: The BPI has excellent psychometrics [86-92] and is recommended by the IMMPACT group for the assessment of pain in clinical trials. [75] The developers of the BPI recommend BPI SF-3, the "pain worst" rating, as the primary response metric. The question asks participants to rate their worst pain in the prior 7-d on a 0 to 10 NRS, where "0" indicates "No pain" and "10" indicates

“Pain as bad as you can imagine.” In order to gain a more comprehensive assessment of participants’ pain experience, daily least pain (BPI SF-4), daily average pain (BPI SF-5) and daily present pain (BPI SF-6) after morning ADLs are also collected. To analyze successful treatment, short-term responders will be defined as those who have a clinically meaningful 30% reduction of pain [72] at end of treatment. Long-term responders will be those who continue to have 30% reduction at weeks 8 and 12. The investigative team has extensive experience with the BPI. [2, 5, 8, 10, 11, 13, 70, 71, 93, 94]

Pain interference with ADLs – BPI SF-9: BPI SF-9 specifically evaluates the impact of pain on ADL performance within 7 domains of daily activity over a 7-day period: general activity, mood, walking ability, normal work, relations with other people, sleep and enjoyment of life on a 0-10 NRS, where 0 indicates “does not interfere” and 10 indicates “completely interferes.” [124] The BPI SF-9 score is the average of the scores for the 7 domains. Psychometrics have been evaluated as part of the BPI battery. [86-89] BPI SF-9 has been used to evaluate the impact of percutaneous PNS mediated pain reduction on ADLs. [6, 8, 11, 13, 62, 70]

QoL – SF 36: SF-36 is a health related QoL measure that assesses physical functioning, role limitation because of physical health problems, bodily pain, social functioning, general mental health, role limitations because of emotional problems, vitality (energy/fatigue), and general health perception. [125] It is the only reliable and valid measure previously used to assess change in QoL associated with the treatment of shoulder pain with PNS. [6, 9, 13, 71]

Isometric Voluntary Abduction Shoulder Torque (IVAST): IVAST is an objective predictor of strength which is an important factor in ability to complete functional tasks in older adults. [195] IVAST will be measured in an established protocol [96] with a Biodex Biomechanical Measurement System (Biodex Medical Systems, Shirley, NY). Participants will be seated and fastened securely with the abduction axis of the shoulder aligned with the rotational axis of the dynamometer. The arm will be attached to the dynamometer by a strap just above the elbow. The arm will be held at 30 degrees of shoulder abduction and neutral rotation. Participants will be asked to abduct their arm in response to an audio tone. The duration of the audio tone randomly varies between 3 and 5 seconds to prevent the anticipation of the start or end of the cue. The average torque during the last second of the audio tone will be calculated and those values will be averaged over three trials, with 1-minute rest between trials. Abduction torque measurement via Biodex shows high intra- and interrater reliability. [97]

Shoulder Kinematic Analysis: An objective measure of glenohumeral and scapular range of motion will be obtained using an optical tracking system (Optotrack Certus, NDI Measurement Science, Ontario, Canada) during the performance of passive and active pain-free shoulder abduction rotation while seated. Active LED markers will be mounted on the sternum, scapula, upper arm, and forearm. Digitization of bony landmarks on the thorax, scapula, and humerus permit transformation of sensor data into local segment coordinates according to standard protocol. Custom software will be used to extract angular data from the sensors and calculations will be made following the recommendations of the International Society of Biomechanics, Shoulder Group. [98] The extracted angular data includes: 1) peak humeral elevation and 2) Peak scapular tilt. Analysis in post-stroke shoulders is a reliable and valid measure of impairment. [99, 100]

Fugl-Meyer Motor Assessment, upper limb (optional): If PNS reduces HSP by reducing motor impairment, then Fugl-Meyer Motor Assessment (FMA) scores should improve. The FMA was derived from the Brunnstrom Stages [126] of post-stroke motor recovery. Each test element will be graded on a 3-point ordinal scale and summed to provide a maximum upper limb score of 66. Reliability and validity have been demonstrated. [127-129] The FMA will be administered while the subject was seated.

Mechanical Pain Thresholds for Hyperalgesia: The PPTs will be measured with a hand-held Wagner Instruments FPIX Digital dynamometer (Wagner Instruments, Greenwich, CT) with 1 sq-cm rubber tip. The PPT is defined as the amount of force (applied at a rate of 1 kg per second) required to produce a sensation of pain distinct from pressure or discomfort. The 3 sites are the mid-belly of the deltoid muscle of the affected and non-affected limb and the mid-belly of the tibialis anterior of the contralateral limb. Three readings will be averaged at each site. The reliability and validity of the pressure algometry to evaluate deep somatic tissue sensitivity have been demonstrated [101-103], and the method has been used to evaluate central sensitization in numerous pain conditions [104-114], including chronic shoulder pain. [19, 20]

Pinprick pain thresholds for Hyperalgesia (optional): Pinprick thresholds will be measured at the same sites using weighted pinprick stimuli that exert forces of 8, 16, 32, 64, 128, 256, and 512 mN (PinPrick Stimulators, MRC Systems GmbH, Heidelberg). [115, 116] The stimulators will be applied at a rate of 2 s on, 2 s off in an ascending order until the first percept of sharpness is reached. The final threshold will be the geometric mean of five series of ascending and descending stimuli. Pinprick pain threshold has been used to evaluate central sensitization in numerous conditions [117-120], including chronic shoulder pain. [19, 20]

The perceived magnitude of a single pinprick stimulus will be compared with that of a train of 10 pinprick stimuli of the same force (256mN OR 512mN) repeated at 1/s rate at the same sites. The use of the larger stimuli will be made if, when presented at the first test site, the perceived pain rating is "0" for the lesser of the two. Thus, a greater differentiation of response may be possible, but will not present a significant discomfort to the subject. In all tests, the subject can stop the testing procedures. Single pinprick stimuli will be alternated with a train of 10 stimuli until both are done at three different sites: affected shoulder, unaffected shoulder, and unaffected tibialis anterior (lower leg). The mean pain rating of trains divided by the mean pain rating to single stimuli will be calculated as wind-up ratio (WUR). [116]

Several other outcomes measures also will be optional and may not be completed if the testing is found to take an excessive amount of time or if the subject is, for any reason, unable or unwilling to complete all of the testing. These include:

Tactile/touch detection thresholds will be measured using stimulus presentations of graded TouchTest von Frey monofilaments (North Coast Medical) at each test site. Using the ascending method of limits, the lowest force monofilament will be presented to the subject who will respond as to whether or not he/she felt the stimulus presentation, and increasing forces will be presented until the subject responds that he/she felt the stimulus. The second series of stimulus presentations will use the descending method of limits in which a stimulus force that is above threshold level will be presented and decreasing levels of force will continue to be presented until the subject indicates that he/she can no longer feel the stimulus. A second ascending and then a second descending series of stimulus presentations will occur, so that four estimates of threshold will be obtained at each site.

Vibration detection thresholds will be measured using the VSA 3000 Vibratory Sensory Analyzer component of a TSA-II Neurosensory Analyzer (Medoc, LTD; cleared commercially under K922052). The flat probe tip (1.22 sq cm) of the vibratory device will be held lightly against the skin, and the amplitude of the (100Hz) vibration will slowly increase until the subject reports that he/she can feel the vibration. Three trials will be performed at each test site.

Thermal detection and thermal pain function measures will be performed also using the TSA-II Neurosensory Analyzer. Thermal stimuli will be delivered via a thermal probe with contact area between 2.5 sq cm and 9 sq cm. The probe will be held lightly against the skin as the temperature increases (for warm detection and hot pain thresholds) or decreases (for cool detection and cold pain thresholds) from a baseline temperature that approximately matches the neutral skin surface temperature (32°C). Subjects will be instructed to verbally respond when the desired sensation is reached. (For example, during cool detection threshold trials, subjects will be instructed that the temperature will slowly change from a neutral temperature, and that they should tell us as soon as they detect any change in temperature at the test site. For cold pain threshold trials, subjects will be told that the temperature will slowly change from a neutral temperature, and that they should tell us as soon as they feel the sensation increase to a level that they would call painful.) Each type of sensation threshold (cool detection, warm detection, cold pain, hot pain) will be measured three times at each test site.

Temporal Summation of repetitive thermal stimuli will be assessed using the TSA-II Neurosensory Analyzer in a way comparable to Temporal Summation of repetitive pin-prick stimuli described earlier. The perceived magnitude of a single thermal stimulus will be compared with that of a train of 10 thermal stimuli of the same magnitude repeated at a 1/s rate at the same sites. The mean pain rating of trains divided by the mean pain rating of single stimuli will be calculated as wind-up ratio (WUR).

Conditioned Pain Modulation (CPM) is measured using a diffuse noxious inhibitory control (DNIC) protocol and analyzed through established methods. [121] The "test-stimulus" is a 7-sec presentation of a thermal noxious stimulus (between 43-49°C) to the volar forearm of the nonparetic limb, and the "conditioning stimulus" is the

immersion of the nonparetic foot/distal leg into a cold-water bath (12°C) for 60 sec. Pain intensity ratings of the test stimulus occur prior to the conditioning stimulus ("baseline" pain rating), and 40 sec after the conditioning stimulus is initiated ("conditioned" pain rating). The extent of CPM is calculated by subtracting the conditioned pain rating from the baseline pain rating of the test stimulus. [121]

Other: Five other surveys also are collected once each for either eligibility determination or potential correlative data analysis. These are the Mini Mental State Exam (MMSE), the Beck Depression Inventory (BDI), the Pain Catastrophizing Scale (PCS), the Fear Avoidance Beliefs Questionnaire (FABQ) and a Patient Global Impression of Change (PGIC) Assessment.

Concomitant Therapies: Participants may not receive additional PT or OT for pain during the treatment period or during follow-up, but PT or OT for function is permitted. Similarly, they may not receive any injections, or any other forms of electrical stimulation, including TENS or surface PNS, to the affected shoulder. Due to ethical considerations, use of non-opioid and opioid analgesics for pain management will be allowed. Participants may adjust dosing of these medications, but it is preferred that they not change or add medications during the protocol. Participants will maintain their dosage during the week prior to each visit to match the recall period for assessment of BPI SF-3 and 9. Medication use is monitored via diary.

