8.5 Does this study only involve the use of existing/retrospective data/specimens?

Check yes or no.

No

8.6 Describe in detail the study design also known as the experimental flow. Include all study procedures a subject will go through, in order of sequence and timing, including frequency of visits, duration of visits, length of subject participation etc. Please Note this needs to be written for an educated person who is not an expert in the field, do not exceed 300 words:

This is also known as NIH Experimental Procedure section or Clinical Trial Procedure/Experimental Flow section. Do not just attach documents in response to this question you must do a study design summary for IRB Review.

The duration of each subject's participation will be ~4 months.

Visit 1 – Consent/Eligibility: Consent form signed; assessed for eligibility per inclusion/exclusion criteria; MMSE administered; BDI, PCS & FABQ administered; medical history, demographics, comorbidities, and medication use recorded; blood drawn for INR (in applicable subjects); pregnancy test (in applicable subjects). (~3.5 hrs)

Visit 2 – Baseline Outcomes Assessment: Study outcome measures (see Outcomes Assessment) administered to establish baseline levels. (~4 hrs)

Visit 3 - Sprint MicroLead (Electrode) Implant Procedure: Testing of muscle response with Sprint Test Needles; Implantation of percutaneous Sprint MicroLead. Subject given instructions on care of Lead exit site. Skin checked, subject queried for medication usage. Randomization to treatment group. Subset of study outcome measures (questionnaires only) administered. (~2.5 hrs)

Visit 4 - 48-72 hour Post-Implant Safety Check: Check the Lead exit site within 48-72 hours of the Implant procedure; dressing changed. (~1 hr)

Visit 5 - Start of Stimulation: Collection of parameter data; programming of external stimulator (Sprint Stimulator). Subject given instructions on use of System and care of Lead exit site. Skin checked, dressing changed, subject queried for medication usage and adverse events. Subset of study outcome measures (BPI-SF only) administered. (~2 hrs)

Phone Call #1 – One week after starting stimulation, subject queried on condition of Lead exit site, pain, adverse events. (30 min)

Phone Call #2 – Two weeks after starting stimulation, subject queried on condition of Lead exit site, pain, adverse events. (30 min)

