11.2 Anticipated number of subjects (all sites): [enter a number]

30

Anticipated number of subjects to be enrolled at MHS: [enter a number]

30

Anticipated number of potential subjects to be approached: [enter a number]

100

11.3 If this is a multi-site study, how many sites will there be? [enter a number]

How many total sites?

11.4 Subject Characteristics:

Subject Population Categories

Outpatients

Patients with the "disease in question"

Check all that apply

11.5 Subject Source:

Subject Source Characteristics

Subjects from the Practice of the Principal Investigator

Subjects referred or recruited from other physicians practices

Public subject recruitment by advertisement, flyers, websites etc. (Note: required IRB review and approval)

Check all that apply

11.6 If "other" list above in either 11.4 or 11.5 please describe:

If applicable please describe.

View: 12-00 Study Participant Information II

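### Read literally, the stated allocation rule is minimisation with chance only at ties, so about two thirds of the 30 assignments would be fully determined; a stated random element below 1 would be better

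*Protocol*

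**What the plan says.** Section 8.4 of the protocol (Baseline Variables and Randomization) names the method: "Participants are assigned to treatment groups using an adaptive randomization algorithm [76-78] to minimize group imbalances on key patient characteristics". The characteristics are baseline pain (above 6, or 6 and below), pain duration (split at 18 months) and age (split at 55 years). It then describes how the method works: "For each assignment, the algorithm calculates the balance of these variables across the groups", and it "makes an assignment that would result in greater balance in the variables across groups". The section gives no assignment probability, tie rule or imbalance measure, and does not say who runs the algorithm or sees its output.

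Other facts that bear on the point:

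- Size and arms (8.4, Study Summary): "Thirty subjects will enroll and receive a 3-week course of percutaneous IM PNS at one of 3 doses". The arms differ in daily stimulation time: "participants receive 3h, 6h, or 9h of stimulation each day".
- Site (11.2): the total and the number at this centre are both 30.
- Timing (8.6): eligibility is settled at Visit 1 and baseline outcomes are taken at Visit 2. Visit 3 lists the lead implant and then "Randomization to treatment group. Subset of study outcome measures (questionnaires only) administered".
- Recruitment (11.2 and 13.3): about 100 people are to be approached. Respondents are first screened informally, possibly by telephone.

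**The concern.** A rule that always takes the best-balancing arm leaves little to chance. Once earlier assignments and the three factor levels are known, the next arm can often be worked out before the participant is allocated. All three factors are available by Visit 2, and age and pain duration could be learned at telephone screening. The staff who program 3, 6 or 9 hours a day necessarily learn the arms of the participants they treat.

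The main risk is selection. If the next arm is foreseeable, it can influence who is encouraged to come in and when they are scheduled, even without intent. About 10 participants per arm and a self-reported primary outcome give little room to absorb a few steered entries. A rule with almost no chance in it also weakens the basis for randomization-based inference.

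**Working it through.** The protocol states no predictability figure, so there is none to reproduce. The literal rule was simulated.

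**Inputs from the protocol:** 3 arms; 3 two-level factors; N = 30; the rule applies to every assignment.

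**Assumptions, because the protocol is silent:** equal factor weights; imbalance measured by the range or the variance of arm counts within the participant's factor levels; ties broken at random; several sets of factor prevalences (0.5/0.5/0.5, 0.7/0.6/0.7 and 0.7/0.5/0.85). There were 1,500 simulated trials per setting.

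**How the rule works (range measure, three participants with the same factor levels).**

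- First participant: each arm would give a range of 1 on each factor, a total of 3, so all three arms tie. Suppose arm A is drawn.
- Second participant: counts on each factor are (1,0,0). Adding to A gives (2,0,0), total 3 × 2 = 6. Adding to B or C gives a range of 1, total 3. The choice is narrowed to two arms. Suppose B is drawn.
- Third participant: counts are (1,1,0). Adding to A or B gives a range of 2, total 6. Adding to C gives (1,1,1), total 0. C is certain.

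**Literal rule, N = 30.**

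| Measure | One best arm | Two tied | Three tied | Correct guesses |
|---|---|---|---|---|
| Range | 68-69% | 25% | 6% | 83% |
| Variance | 64% | 27-28% | 9% | 80-81% |

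A fully informed guesser is right with certainty when one arm is best, half the time in a two-way tie and a third of the time in a three-way tie. For the range measure with prevalences of 0.5: 0.688 + 0.249/2 + 0.064/3 = 0.834. For the variance measure: 0.635 + 0.275/2 + 0.090/3 = 0.80.

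In participants, 0.64 × 30 to 0.69 × 30 is about 19 to 21 of 30 fully determined. Correct guesses number 0.80 × 30 to 0.83 × 30, or about 24 to 25, against 10 by chance. Results barely move with factor prevalence. If total arm size is balanced as well, 71-76% are determined and 85-87% guessed.

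**With a random element.** Let the best arm (or tied best arms) have probability p.

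| p | Correct guesses | Mean within-factor spread | Largest minus smallest arm |
|---|---|---|---|
| 1.0 (literal) | 80-83% | about 0.8 | 0.4-0.5 |
| 0.8 | 67-69% | about 1.4 | 1.3-1.4 |
| 0.7 | 59-61% | 1.7-1.8 | 1.7-1.9 |

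Spread is the largest minus the smallest arm count within a factor level, averaged over the six levels. Check at p = 0.8, range measure: 0.8 × 0.726 + 0.8 × 0.216/2 + 0.058/3 = 0.687.

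**The case against.** The strongest reply is that the sentence is a short summary in an ethics application form. The protocol says "Participants are assigned to treatment groups using an adaptive randomization algorithm" and cites three sources for it, and those sources may specify a biased coin. Assignment probabilities and tie rules are also often left to a separate randomization document. This stands in part. A reader might infer that the trial's allocation has no random element at all. The protocol does not support that: it shows only that the one rule it writes down contains none, and even that rule needs some way to settle ties. What remains is that the protocol did choose to state the rule, for every assignment, and stated it in a deterministic form.

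The second reply is that the 80-83% assumes someone who holds every earlier allocation, every earlier participant's factor levels and the imbalance measure. Nothing in the protocol says anyone does. This stands: the figure is an upper bound. Knowledge of earlier arms is plausible for treating staff at one site, but it is an inference.

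A reader might also infer that predictability would distort lead placement, the Visit 3 questionnaires or assessor blinding. The support is thin. Placement is described identically for all arms, the Visit 3 questionnaires are listed after assignment and are not the Visit 2 baseline, and a blinded assessor would not hold the earlier allocations needed to predict. Assessor blinding is a secondary concern at most.

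Last, a biased coin at 0.8 still leaves about two thirds of assignments guessable. That is correct; the change reduces predictability and does not remove it.

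**Conclusion.** The concern holds in a limited form. The only allocation rule in the protocol, read literally, is minimisation with chance only at ties. At one site with 30 participants and three arms, about 64-69% of assignments would then be fully determined, and up to about 80-83% could be guessed by someone with full information. These figures rest on equal weights, a range or variance measure and random tie-breaking, and they are stable across the prevalences tried. They do not show that the program in use lacks a random element, or that any staff member could in fact predict. This is an inexpensive improvement to a stated rule, with influence on entry and its timing as the main risk; it is not evidence that the allocation was compromised.

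**What to change.** Replace the rule sentence in section 8.4 with one stating that:

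- the best-balancing arm is assigned with a stated probability below 1 (0.8 or 0.7 are examples), the other arms sharing the remainder;
- ties are broken at random;
- the imbalance measure is named;
- the program releases the assignment only after baseline data are locked, and enrolling staff cannot see the next arm.

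If the cited algorithm already has these features, correct the sentence to describe them. If enrolment is over, record the probability actually used.

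The cost is some balance. Mean within-factor spread rises by about 0.6 of a participant at 0.8 (0.8 to 1.4) and by about 0.9 to 1.0 at 0.7 (0.8 to 1.7-1.8). Correct guesses fall to about 67% or 60%, still well above 33%. Withholding the next arm and the running list from enrolling staff therefore matters as much as the probability chosen.
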